## 2. LAY SUMMARY

The standard for diabetes management is changing. What was previously thought to be a lifelong progressive condition to be managed primarily with increasing doses of medications, may instead be put into remission (achieving normal or near-normal blood glucose levels without medications) if treated with intensive weight loss support. However, the majority of patients with type 2 diabetes still rely on general dietary advice from primary care professionals. While there is considerable uncertainty regarding the optimal diet composition for people with type 2 diabetes, there is a growing interest from patients, practitioners and the general public in using real-food, low carbohydrate diets to achieve weight loss, improved glycaemic control and even disease remission. A recent small-scale study demonstrated that it was possible, and effective in the short-term, for practice nurses in primary care to support patients with type 2 diabetes to adopt a real-food, low-carbohydrate weight loss diet. However the patients and healthcare professionals who took part in this study were keen to know whether digital interventions and app-based

support could be an alternative way to achieve the same results, with the potential for more frequent support without increasing the demand on the primary care workforce. This study aims to investigate whether an app-based low-carbohydrate intervention with remote behavioural support is effective at improving glycaemia, weight, and other markers of cardiometabolic risk, for people with type 2 diabetes in primary care.

### 3. SYNOPSIS

Study Title	Testing the effectiveness of low carbohydrate diet with remote support for patients with type 2 diabetes in primary care, on weight and glycaemic control: a randomised controlled trial		
Internal ref. no. / short title	Low Carb App		
Study registration	Clinicaltrials.gov: NCT04916314		
Sponsor	University of Oxford		
Funder	NIHR Oxford Biomedical Research Centre (BRC) Wellcome Trust		
Study Design	Individually randomised controlled trial		
Study Participants	Adult men and women with type 2 diabetes and $\text{BMI} \geq 27\text{kg/m}^2$ (30 if recorded as white ethnicity)		
Sample Size	100 (50 intervention, 50 control)		
Planned Study Period	01/08/2021 – 01/10/2023 Per participant: 12 months		
Planned Recruitment period	01/08/2021-31/12/2021		
	Objectives	Outcome Measures	Timepoint(s)
Primary	To determine the effectiveness of an app-based programme offering support for a low energy, low carbohydrate diet on glycaemia, compared with usual care in people with type 2 diabetes	Change in participants' HbA1c from baseline to 3 months and baseline to 1 year (co-primary outcomes)	Baseline, 3 months, 1 year
Secondary	
 
To determine the effect of an app-based programme offering support for a low energy, low carbohydrate diet on remission of type 2
 
	Number of participants meeting consensus definition for remission from	1 year

	
diabetes compared with usual care
 
 
• To determine the effect (Short- and longer-term) of an app-based support programme for dietary change in type 2 diabetes on weight, compared with usual care
 
• To determine the effect of an app-based programme offering support for a low energy, low carbohydrate diet on other markers of cardiometabolic risk, compared to usual care
 
• To determine the effect of an app-based programme offering support for a low energy, low carbohydrate diet on diabetes related distress and quality of life
 
	
type 2 diabetes at 1 year
 
Change in participants' weight from baseline to 3 months and baseline to 1 year
 
Change in participants':
 
 
- Blood pressure (systolic and diastolic)
 
-Lipid profile (total-, HDL- and LDL- cholesterol, triglycerides)
 
-Liver function (Bilirubin, ALT, ALP, Albumin)
 
 
Change in participants' PAID score and EQ5D
 
Interviews with participants
	
Baseline, 3 months, 1 year
 
Baseline, 3 months, 1 year
 
Baseline, 3 months, 1 year
 
3 months

Process Measures	
 
• To examine engagement with the programme
 
	
 
• Data will be collected on measures of engagement with the three main components of the programme ("Learn", "Track", and "Support"), via the app programme, and change in dietary
 
	Baseline, 3 months, 12 months

	
 
• To examine the demographic profile of participants
 
• To explore participants' experience of using the app-based support
 
	intake patterns (via Intake24 24 hour dietary recall questionnaire) 
 
• Data (age, gender, ethnicity, level of education, deprivation index, dietary preference) will be collected via questionnaire
 
• Interviews with participants
 
	Baseline
Intervention(s)	"SecondNature" App: remote support for a low-carbohydrate dietary intervention for weight loss		
Comparator	Usual care		

#### 4. ABBREVIATIONS

CI	Chief Investigator
CRF	Case Report Form
CTRG	Clinical Trials & Research Governance, University of Oxford
FBC	Full Blood Count
GCP	Good Clinical Practice
GP	General Practitioner
HbA1c	Glycosylated Haemoglobin A1c
HRA	Health Research Authority
ICF	Informed Consent Form
IG	Information Governance
LFTs	Liver Function Tests (Bilirubin, ALT (Alanine aminotransferase), AST (Aspartate aminotransferase), ALP (Alkaline Phosphatase), Albumin)
NHS	National Health Service
RES	Research Ethics Service
OXTREC	Oxford Tropical Research Ethics Committee
PI	Principal Investigator
PIL	Participant/ Patient Information Leaflet
R&D	NHS Trust R&D Department

REC	Research Ethics Committee
SOP	Standard Operating Procedure
T2DM	Type 2 diabetes mellitus

## 5. BACKGROUND AND RATIONALE

There are an estimated 4 million people living with type 2 diabetes (T2D) in the UK, with numbers expected to rise to 5 million by 2025 (1). Globally, almost 15% of all deaths are attributable to diabetes in the 20-79 years age group, with 47% of those deaths occurring in people under 60 years of age(1). Currently, 10% of the NHS annual budget is spent on diabetes (around £10 billion).

But the paradigm for T2D management is changing.(2) What was previously thought to be a lifelong progressive condition to be managed primarily with escalating doses of medications, may instead be put into remission if treated with intensive weight loss support(3). However, the majority of patients with type 2 diabetes still rely on general dietary advice from primary care professionals. There is considerable uncertainty regarding the optimal diet composition for people with T2D, but there is a growing interest from patients and practitioners in using real-food, low carbohydrate diets to achieve weight loss, improved glycaemic control and even disease remission.

In our previous DIAMOND study, a randomised controlled feasibility trial (n=33), we demonstrated that it was feasible and acceptable for practice nurses to support patients with T2D to adopt a real food, low-energy, low-carbohydrate weight loss diet in primary care. On average, participants in the intervention group achieved clinically significant improvements in weight and HbA1c in the short-term (12 weeks)(4). Recruitment was from April-October 2018; Participant follow up appointments were from August 2018-February 2019. Participants received no further formal support or intervention after the 12 week period.

After study completion, healthcare professionals and participants in qualitative interviews expressed an interest in whether the programme could be expanded to include app-based or other remote support. Patients were keen to consider increased levels and modes of support, and the potential for a synchronous “community” of participants to support each other, while practitioners were concerned about adequate workforce capacity and time constraints of delivering increased contacts within primary care.

With increasing interest in remote monitoring and digital support options during the Covid19 pandemic, as well as the NHS Long Term Plan’s focus on development and support of digital interventions, this question has become increasingly relevant. Many programmes aiming to support weight loss and improvement in control of T2D – or even disease remission – are based on evidence from trials of programmes with in-person support. However, when it comes to wider commissioning or roll-out in routine care, such programmes are often expanded to include digital delivery of the interventions (such as in the National Diabetes Prevention Programme, and Diabetes Remission Total Diet Replacement Pilot), sometimes without clear randomised controlled trial evidence that digital versions of the programmes will have similar effectiveness.

There is a growing support from observational evidence to suggest that remote support via a digital platform can positively affect the weight and glycaemia of patients with type 2 diabetes who engage with these interventions. One such platform offering remote behavioural and dietary support for people with type 2 diabetes provides a three-month remote behavioural change programme with mentoring from a registered dietitian or nutritionist (health coach), encouraging adoption of a low energy, low-carbohydrate diet, peer group support, structured education articles and activity tracking technology. These elements are accessed via a smartphone or web-based application; each participant additionally receives an instructional handbook, and recipe book (+/-wireless weighing and activity tracking technology). A service evaluation of 190 participants referred as part of routine care from January to July 2018 found that 75% of patients (n=144) started the programme, and 65.3% (94) of these submitted weight readings after 12 months. Of these, 60% achieved over 5% total body weight loss, and 28.7% achieved over 10% body weight loss; the average total 12 month weight change was -7.8kg (+/- 8.6kg). 28.5% of participating patients attended for a blood test with their GP after 12 months as part of routine care; in those with available HbA1c data, there was a statistically significant change in HbA1c compared to baseline (mean -10.4mmol/mol, SD +/- 8.6mmol/mol)(5). An earlier larger cohort of 896 patients who completed a similar programme (3 months of “core” support, plus ongoing access to sustainable advice and encouragement of weekly engagement) over a 1 year period, comprising both self-funded clients and those referred by their GP free of charge, found a significant change in mean weight of -7.12kg (SD 6.37kg) at 6 months and -6.14kg (SD 9.97 kg) at 12 months compared to baseline measures(6). While the weight and glycaemic changes reported appear promising, and clinically significant, these observational studies have several key limitations (including the generalisability of the patient population (a selected group of people with high intrinsic motivation to take part, often in locally limited geographical areas); observational design and lack of a control or comparator group; and significant loss to follow up and absence of follow up data, without the ability to determine why) that preclude drawing reliable conclusions as to the programme’s performance and effectiveness.

Therefore, the aim of this study is to test in a randomised controlled trial whether a low energy, low carbohydrate diet delivered via remote support is effective at improving glycaemia, weight, and other markers of cardiometabolic risk, for people with type 2 diabetes in primary care.

Understanding changes in clinical outcome measures and participant behaviours could inform future programmes to support people with type 2 diabetes in primary care.

## 6. OBJECTIVES AND OUTCOME MEASURES

Objectives	Outcome Measures	Timepoint(s) of evaluation of this outcome measure (if applicable)

Primary Objective To determine the effectiveness of an app-based programme offering support for a low energy, low carbohydrate diet on glycaemia, compared with usual care in people with type 2 diabetes	Change in participants' HbA1c from baseline to 3 months and baseline to 1 year (co-primary outcomes)	Baseline, 3 months, 1 year
Secondary Objectives 
 
To determine the effect of an app-based programme offering support for a low energy, low carbohydrate diet on remission of type 2 diabetes compared with usual care
 
To determine the effect (Short- and longer-term) of an app-based support programme for dietary change in type 2 diabetes on weight, compared with usual care
 
To determine the effect of an app-based programme offering support for a low energy, low carbohydrate diet on other markers of cardiometabolic risk, compared to usual care
 
To determine the effect on diabetes related distress and quality of life
 
	Number of participants meeting consensus definition for remission from type 2 diabetes at 1 year  Change in participants' weight from baseline to 3 months and baseline to 1 year  Change in participants': - Blood pressure (systolic and diastolic) - Lipid profile (total-, HDL- and LDL- cholesterol, triglycerides) - Liver function (Bilirubin, ALT, ALP, Albumin)  Change in participants' PAID score and EQ5D,	1 year  Baseline, 3 months, 1 year  Baseline, 3 months, 1 year  Baseline, 3 months, 1 year  Baseline, 3 months, 1 year
Process Measures To examine engagement with the programme	Data will be collected on measures of engagement with the three main components of the programme ("Learn", "Track", and "Support"), via the app programme, and change in dietary intake	Baseline, 3 months, 12 months

To examine the demographic profile of participants	patterns (via Intake24 24 hour dietary recall questionnaire) Data (age, gender, ethnicity, level of education, deprivation index, dietary preference) will be collected via questionnaire	Baseline
To explore participants' experience of using the app-based support	Interviews with participants	3 months

## 7. STUDY DESIGN

This is an individually randomised controlled trial. Participants, recruited via GP practices, will be randomised 1:1 with simple randomisation and no stratification to either the intervention group or control (usual care). They will be enrolled in the study for 1 year, of which the intervention (dietary support via the app) will run for 3 months. Most study procedures will be conducted online or remotely (by telephone) including: screening, eligibility assessment, informed consent, randomisation, engagement with the app-based intervention. Participants will be asked to attend 3 face to face appointments for the research study at their local GP practice for measurements to be taken (weight, blood pressure) and blood tests, at baseline, 3 months and 1 year, and will have 1 additional telephone contact with their GP or practice nurse before starting the intervention. Face to face appointments will be incorporated with routine clinical appointments when possible.

A flow diagram showing the trial design is given in Appendix A

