### **8.3. Exclusion Criteria**

The participant may not enter the study if ANY of the following apply:

- Unable to understand the study materials and interventions
- Currently following a weight loss programme (defined as a structured, prescribed and monitored programme and not a self-directed weight loss attempt)
- Pregnant, breastfeeding, or planning to become pregnant during the course of the study
- History of bariatric surgery, including gastric banding
- Currently using insulin therapy
- Proliferative diabetic retinopathy, or maculopathy.
- Recent myocardial infarction or stroke (<3 months)
- Renal failure (chronic kidney disease stage 4 or 5)
- Current active treatment for cancer (other than skin cancer treated with curative intent by local treatment only)
- Their doctor does not feel they are appropriate to participate for another reason (e.g. active eating disorder diagnosis, significant psychological disturbance)

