### **1. Online:**

Participants will be asked to complete a baseline questionnaire requesting demographic information and their current medication, and the standard questionnaires that will be used in the study (the Problem Areas in Diabetes (PAID) score, the EQ5D (quality of life assessment), and a 24 hour dietary recall questionnaire (“Intake24 dietary assessment tool”, where participants are asked to record all food and drink intake in the last 24 hours). This will also further assess whether people are sufficiently able to complete online trial procedures, and only those who complete the questionnaire will be randomised. Participants will be informed in the Participant Information Sheet that they will only be able to enter the study after completing each individual questionnaire fully in one attempt as the system will not allow them to go back into each

questionnaire to answer the remaining questions later. Overall there are 3 questionnaires for each participant to complete. These should take less than 30 minutes to complete. Patients will be able to fill in the baseline questionnaires and 24 hour dietary recall at any time after completion of the online consent form but before the appointment at their GP practice, as long as they complete each questionnaire in one attempt. Should a participant not complete their questionnaires, reminder emails will be sent at one and two weeks after they received the initial invite to complete the questionnaires.

2. At the GP practice (visit 1)

Having completed the online assessment, participants will be asked (via message on their screen on completing the assessment, and followed up via email) to book the in-person portions of their baseline assessment at their GP practice for measures which cannot be conducted online. At this appointment (with a nurse or healthcare assistant), their height, weight and blood pressure will be measured and recorded, and a blood sample taken for baseline values (HbA1c, lipid profile, liver function tests). Once their practice confirms they have attended this appointment they will be sent a link to the randomisation system.

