#### **9.4. Randomisation and blinding**

All eligible participants will be individually randomised to one of two arms: Intervention (12 week, app-based dietary support), or control (usual care; no active additional intervention). The randomisation will be conducted using the Redcap inbuilt randomisation software. This ensures full allocation concealment as information on future allocations is not accessible to the person randomising.

The participants will be aware that they will be randomised to either an app-based support programme or control, therefore no blinding can take place. Due to the nature of the intervention it will not be possible to blind members of the study team to participant allocation. A letter will be provided to the participant's GP to inform them of which group the participant has been allocated to.

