#### **9.5. Description of study intervention and comparator**

##### **9.5.1. Intervention group**

Participants randomised to the intervention group will receive an email informing them they have been assigned to the intervention group, and that their contact information (name and email) has been securely passed to the provider, who will contact them to process the programme onboarding and account creation. They will contact the participant with information how to download and access the app-based intervention. Thereafter, any identifiable information required by the programme provider application will be provided by the participant. The intervention involves diet, activity and behaviour change components. It comprises a three-month remote behavioural change programme with mentoring from a registered dietitian or nutritionist (health coach), peer group support, structured education articles and activity tracking technology. These elements are accessed via a smartphone or web-based application. Each participant will also receive a hard copy of an instructional handbook and a recipe book.

Participants randomised to the intervention group will also receive 1 additional telephone appointment with their GP or practice nurse, towards the start of the 12 week intervention period, to review their current medications and assess any changes to their medication regime may be warranted in view of their anticipated participation in the programme and planned weight loss. We will provide clinicians with current best practice guidelines they may wish to consider but the decisions for individual patients will remain with their clinician.

For participants in the intervention group, data on participant engagement with the app will be received from the company under appropriate agreements. These data will include (as examples) measures of engagement with the three main components of the programme: Learn, Track, and Support. “Learn” interactions are defined as the number of articles read by participants; “Track” interactions are defined as the number of times a participant registered or viewed weight readings; “Support” interactions are defined as the number of messages sent or read in either the private or group chat channels.

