#### **9.5.2. Control group**

Participants randomised to the control group will receive no additional intervention, and will continue to receive their usual NHS diabetes care from their general practice.

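### Section 7 puts the extra GP or nurse telephone contact before the intervention starts; Section 9.5.1 and, apparently, Appendix B allow the medication review after the diet has begun

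*Combined protocol and SAP*

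**What the plan says.** **Section 7 (Study Design).** Participants "will have 1 additional telephone contact with their GP or practice nurse before starting the intervention". The sentence names neither an arm nor a purpose.

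**Section 9.5.1 (Intervention group).** Those allocated to the app receive "1 additional telephone appointment with their GP or practice nurse, towards the start of the 12 week intervention period". The purpose is to look at current drugs and decide whether the regimen should change "in view of their anticipated participation in the programme and planned weight loss". Clinicians are offered best-practice guidance and keep the decision.

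**Section 9.5.1, onboarding.** On the provider's role, the allocation email tells the participant: "their contact information (name and email) has been securely passed to the provider, who will contact them to process the programme onboarding and account creation". The review is not mentioned among these steps.

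**Section 9.5.2 (Control group).** "Participants randomised to the control group will receive no additional intervention".

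**Appendix B.** One telephone medication check is listed, footnoted as applying to the intervention group only. As far as the broken table can be read, it is marked in the same column as app engagement, which appears to be months 0-3.

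**Related provisions.** Section 8.3 excludes anyone "Currently using insulin therapy" and no users of any other glucose-lowering drug. Section 9.3 collects medication at baseline: "Participants will be asked to complete a baseline questionnaire requesting demographic information and their current medication". Section 9.4 provides a letter to the participant's "GP to inform them of which group the participant has been allocated to".

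**The concern.** The review exists because drug doses may need to change when a person with type 2 diabetes starts a low-energy, low-carbohydrate diet and expects to lose weight. It serves that purpose best if it comes before the change in diet. One section requires that order, another allows the review to fall inside the intervention period, and the schedule seems to agree with the second. A practice working from Section 9.5.1 or the schedule could make the call in week 1 or 2, after the participant has changed diet.

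What is at stake is participant safety and consistent conduct across about 10 practices. Participants on non-insulin glucose-lowering drugs can enter and could begin the diet unreviewed. Section 10 sets a recording procedure only for serious adverse events, with proactive questioning at 3 and 12 months, so a less serious early problem from an unadjusted dose might not be captured.

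**Working it through.** The plan gives no figure on this point to reproduce. The check of the defect is a comparison of text; the only arithmetic concerns the cost of the remedy.

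**Step 1. Is it the same contact?** Sections 7 and 9.5.1 agree on number (one), mode (telephone) and staff (GP or practice nurse), and both call it additional. Appendix B lists only one such contact and restricts it to the intervention group. Section 9.5.2 gives controls nothing extra. Identity is an inference, but a well-supported one.

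**Step 2. Do the timings agree?**

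| Place | Timing | Review after the diet has begun |
|---|---|---|
| Section 7 | Before the start | Departs from the text |
| Section 9.5.1 | Early in the 12-week period | Fits the text |
| Appendix B | Apparently the 0-3 month column | Appears to fit |

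A review before the start satisfies Section 7 and the purpose given in Section 9.5.1. A review after the start cannot satisfy Section 7.

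**Step 3. Does any other step settle the order?** After allocation, the participant's name and email go to the provider, which begins onboarding; nothing waits for the review. The other safeguards are GP screening of the mailing list (9.1), exclusion at the doctor's discretion (8.3), the allocation letter (9.4), the clinician guidance (9.5.1) and Trial Management Group oversight (13). None of these, as described, sets the sequence. The amendment history says Section 9.5.1 was updated for the referral pathway, which does not bear on timing.

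**Step 4. How many could be affected?** The planned intervention arm is 50. The documents give neither the share on relevant drugs nor the time from allocation to starting the diet. The only bounds are therefore 0 and 50, which is uninformative. The baseline medication questionnaire would let the team count those on relevant drugs.

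**Step 5. What would waiting for the review cost?** Inputs: active programme 12 weeks (Section 9.6), visit 2 at 3 months (Section 9.6), and an assumed wait *d* of 1 or 2 weeks.

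- Three calendar months = 3 × 365.25 / 12 / 7 = 13.04 weeks, so the slack is 13.04 − 12 = 1.04 weeks.
- Visit 2 at 3 calendar months: share outstanding = max(0, 12 + *d* − 13.04) / 12. For *d* = 1 this is 0%. For *d* = 2 it is 0.96 / 12 = 8.0%.
- Visit 2 at 12 weeks: share outstanding = *d* / 12. For *d* = 1 this is 8.3%. For *d* = 2 it is 16.7%.
- Sections 7 and 9.5.1 also describe the programme as lasting three months. If programme and visit are both 13.04 weeks, the shares are 1 / 13.04 = 7.7% and 2 / 13.04 = 15.3%, inside the ranges above.

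These figures apply only to a participant who actually waits, and they ignore onboarding time. A review done during onboarding adds no delay.

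**The case against.** **The intended order is clear enough.** Section 9.5.1 speaks of participation that is anticipated and weight loss that is planned, so staff reading both sections have a workable route: review first. This shows a likely purpose but does not set the timing. A reader might infer that Section 7's order is plainly the one intended. Appendix B, as far as it is legible, points the other way, so the documents do not settle that.

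**Late review is an ambiguity, not a permission.** A reader might infer that a practice reviewing medication after the start would be compliant because it follows Section 9.5.1. The documents do not support that. Section 13 requires conduct according to the approved protocol and Section 14 treats any departure from it as a deviation; a late review departs from Section 7. This part of the objection stands.

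**The harm is not sized.** There is no drug profile, no start-up time and no event rate. Passing a name and email to the provider does not start the diet, and onboarding leaves time for the call. The GP letter, clinician guidance and provider agreements are not among the documents and might state the order. All of this stands, and it limits the weight of the point. It does not remove the contradiction in the protocol text.

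**The arithmetic measures the remedy, not the defect.** Correct. It is given only so that the sponsor can see the cost of waiting, and the 0% end depends on reading the programme as 12 weeks and the visit as 3 calendar months.

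**Conclusion.** The inconsistency is real and in current text. Section 7 requires the contact before the intervention; Section 9.5.1 and, apparently, Appendix B allow it within the intervention period; and no onboarding step decides between them. It is a minor-to-moderate patient-safety inconsistency.

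This rests on three things: that the passages describe one contact, which number, mode, staff and the Appendix B footnote support; that the Appendix B column has been read correctly from a damaged table; and that the documents not seen do not already fix the order. Confidence is medium for these reasons.

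Two stronger readings should be resisted. A reader might infer that up to 50 participants will start the diet unreviewed; 50 is simply the planned arm size, and the number affected is not known from the documents. A reader might also infer that the trial's results are at risk; no estimand, power or error rate is affected.

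**What to change.** 1. State in Section 7, Section 9.5.1 and Appendix B that, for the intervention group only, the medication review is completed before the participant begins the dietary change. Use *dietary change* in all three places, so that onboarding and account creation can run in parallel without becoming deviations.
2. Use the existing GP allocation letter to ask for the review promptly. A target such as 7 days would do, for the sponsor to set.
3. Tell participants in the allocation email to wait for the review before changing their diet.
4. Record the review date and the diet start date in the CRF.

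If the sponsor prefers a review within the intervention period, Section 7 should be corrected instead and an explicit window given.

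**Cost.** Wording in three places, one line each in the letter and the email, and two CRF date fields. The referral route in Section 12.2 is unchanged, and no hold on app access is needed. Some participants would start a little later, with the small loss of programme delivered by the 3-month co-primary visit worked out above. They stay in their allocated arm under the intention-to-treat analysis in Section 11.1.
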